### **APPROACH:**

This is a prospective, open label study of SCIG for the treatment of patients with CIDP who are dependent on IVIG for control of symptoms.

**Participants:** Up to 30 patients with IVIG-dependent CIDP will be enrolled. To qualify, a patient must meet **ALL** of the inclusion criteria and **NONE** of the exclusion criteria.

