**Exclusion Criteria:**

- 1) Thrombocytopenia or other bleeding disorders;
- 2) Patients on anticoagulation therapy with an INR > 3.5;
- 3) Severe or anaphylactoid reactions to IVIG;
- 4) Cancer (active or currently treated);
- 5) Pregnancy;
- 6) Breast-feeding;
- 7) Renal insufficiency (creatinine > 1.5 upper limit of normal) or failure;
- 8) Congestive heart failure;
- 9) Psychiatric illness that would interfere with ability to provide informed consent or adhere to protocol;
- 10) Current IVIG doses greater than 2 g/kg per month;
- 11) Subject with an IgA level < 5% lower limit of normal;
- 12) History of active infection with HIV, Hepatitis B or Hepatitis C;
- 13) Presence of any other medical condition, which in the opinion of the investigator might interfere with performance;
- 14) Participation in a trial of an investigational medicinal product for CIDP in the past 12 weeks.

**Sample size and statistical analysis:** Descriptive information for the rate of change, such as mean and standard deviation, will be calculated. Due to the small sample size and self-control used in this study, instead of using paired t-test, Wilcoxon paired ranked test will be used to compare the change of before and after from each patient. Significance level is defined as 0.05 and all of the analyses will be carried by SAS (version 9.2).

**DESIGN:** The study will be submitted to the USF IRB for approval.

**Specific Aim #1.** We will assess QOL using the Medical Outcome Study 36-item short form health status scale (SF-36) and the Rasch-built Overall Disability Scale (R-ODS). The scales have been validated in patients with CIDP (Merkies et al, 2002; van Nes et al, 2011). We will also do a survey of side effects and satisfaction with treatment (using the Treatment Satisfaction Questionnaire for Medication, or TSQM) and CIP-PRO20 scale (used by permission from [name]; see appendix 3). No surveys will be completed until the patient signs the ICF. In addition, we will determine whether patients currently treated with IVIG would be willing to try the SC route of administration. Reasons cited for unwillingness to switch will be collected.

Specific Aim #2. To test the safety and tolerability of SCIG and feasibility of self-administration in patients with CIDP.

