Specific Aim #4. To test the hypothesis that SCIG is efficacious in controlling the symptoms of CIDP.

Clinical response to SCIG will be monitored using HHD and 20-ft timed walk. Data from pretreatment and SCIG treatment phase will be compared. The HHD will measure force generated by the following muscle groups: Shoulder flexion, elbow flexion, elbow extension, wrist extension, first dorsal interosseous (hand), hip flexion, knee extension, knee flexion, ankle dorsiflexion. Measurement will be done bilaterally in duplicates. For the primary efficacy endpoint, HHD muscle strength measured at Week 24 will be compared to HHD muscle strength measured at baseline (pretreatment)

Secondary End-Point.

1. Progression of symptoms requiring reversion to IVIG, initiation of PLEX or other medications, or hospitalization.

**Study Timeline and Feasibility:** Participants will be recruited from the USF Neuromuscular Clinic. This Clinic is the tertiary referral center for the west coast of Florida, with a population of more than 4 million in the Tampa Bay region alone. We estimated that we have more than 70 patients with CIDP. In addition, we see an average of 2 new CIDP patients per month. Thus, there are enough patients for a 3 to 1 screening to enrollment ratio. Planned recruitment is an average of 1 patient every 1.5 months, for a total of 22.5 months. This schedule will place the final recruit completing the trial during month 30 and afford time during the final 6 months of the study for analyzing and preparing data for publication. This planned recruitment timeline is feasible given the size, established referral patterns, and historical recruitment experience of this clinic.

**Rescue protocol:** If a subject worsens (or “relapses”) during the study, we will institute a rescue protocol. Relapse is defined as a 20% decrease in force (as detected on HHD) in more than 50% of the muscles tested when compared to baseline. In case of relapse, we will quantify the serum Ig levels, give IVIG 1 g/kg boost followed by SCIG at 2 g/kg per month. If the subject is already on 2 g/kg per month of SCIG, we will switch the patients back to IV administration and/or institute other treatment options (steroids, PLEX). Please see algorithm in Appendix 2. We will also switch back to IVIG if, at any point during the study:

- a. The subject requests the switch due to treatment failure, adverse events or patient preference.

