- b. The investigators consider it to be in the best interest of the subject (i.e., due to intolerable side-effects, pregnancy, or noncompliance).

**Potential Pitfalls and Alternative Strategies:** There is the potential that some patients may lose interest or become too reticent in performing self-administration. Since compliance may be an issue with self-administration of an injectable medication, serum IgG levels will be done to monitor patient’s adherence to protocol. The use of a home journal for recording therapy and a weekly telephone call will encourage compliance. In the scenario where there is concern with patient compliance, a weekly home therapy visit will be done. Attrition is also expected during the course of the study. If a participant becomes a ‘drop out,’ his or her data will be used in the analysis using an intention to treat protocol. Finally, while recruitment can be an issue in clinical trials, our planned enrollment rate of an average of 1 patient per 1.5 months is feasible. Furthermore, we already identified several patients who are appropriate for this trial. With an average of 2 new CIDP patients seen per month in the USF Neuromuscular Clinic, we should be able to recruit the remaining patients in the proposed timeline. Furthermore, there are many more CIDP patients in the greater Tampa region who are not being seen at USF. Thus, there is an untapped pool of subjects available. In the unanticipated scenario that we fall behind on subject recruitment, we have incorporated 6 additional months in our timeline for analysis and manuscript preparation that could be utilized for subject recruitment and treatment.

**Data Management and Quality Control:** Physiologic and questionnaire data will be collected across two time points (pre- and SCIG treatment phase) by the PI and coordinator who are all proficient in these testing methods. To ensure participant confidentiality, data will be coded to remove patient identifiers into a password-protected database (Excel) on a central computer system that is backed up daily. Data accuracy will be verified by double data entry. All original paper questionnaires will be locked in the PI’s office with only coded identifying information. There will be an interim analysis done after 8 patients have completed the study.

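### The plan gives no value for a patient who cannot walk 20 ft, so loss of walking is not counted in the timed-walk result

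*Combined protocol and SAP*

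**What the plan says.** Specific Aim #4 names two measures of efficacy, hand-held dynamometry (HHD) and the 20-ft timed walk: "Clinical response to SCIG will be monitored using HHD and 20-ft timed walk". The next sentence sets the comparison: "Data from pretreatment and SCIG treatment phase will be compared". Week 24 is fixed as the time point for HHD, the primary efficacy endpoint. No time point is fixed for the walk, which Table 2 schedules at screening, Day 1, Week 1 and monthly from Week 4 to Week 24.

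The test is given under Sample size and statistical analysis: "Wilcoxon paired ranked test will be used to compare the change of before and after from each patient". On the error rate, the same paragraph says "Significance level is defined as 0.05" and does not say whether the test is one- or two-sided.

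On missing data, Potential Pitfalls and Alternative Strategies says "Attrition is also expected during the course of the study", and that for a drop-out "his or her data will be used in the analysis using an intention to treat protocol". It names no method of imputation or scoring.

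The HHD worksheet (Appendix 5) has a box for a patient too weak to do the task. The supplied text contains no walk worksheet and no value for inability to walk.

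**The concern.** A timed walk has no value for a patient who cannot complete it. The walk is then missing because of the outcome being measured. A signed-rank test needs two values per patient, so a patient with no on-treatment time contributes nothing. If an earlier on-treatment time is used instead, the patient stays in the test but is represented by a walk from before the loss.

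The situation is foreseeable. Patients are dependent on IVIG, walking impairment is one of the qualifying features, and the protocol plans for relapse. No eligibility criterion requires the ability to walk 20 ft, so a patient already unable at baseline could also enrol and would form no pair.

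The design is single-arm and before/after, so no control group carries the same loss. Omitting patients who lost walking moves the walking result in one direction, towards the Aim 4 hypothesis. The study is also open label. If the rule is left until the data are in, it would be chosen with knowledge of who stopped walking.

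**Working it through.** The plan states no effect size, SD, power or rate of lost walking for the walk, so it has no figure to reproduce. The checks below show how much the missing rule could matter.

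**Inputs from the protocol**
- Maximum sample size 30 (Approach): "Up to 30 patients with IVIG-dependent CIDP will be enrolled".
- Recruitment plan (Study Timeline and Feasibility): "Planned recruitment is an average of 1 patient every 1.5 months, for a total of 22.5 months". This implies 22.5 / 1.5 = 15 patients, so both N = 15 and N = 30 are shown.
- Significance level 0.05, taken as two-sided.

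**Assumed:** the number of non-walkers, k.

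**Check 1: every remaining walker is faster.** This is a stress case, chosen to show whether the scoring rule alone can change the conclusion.

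*Deletion.* All N − k remaining changes have the same sign, so the exact two-sided p is 2 / 2^(N−k). For N = 15 and k = 2 this is 2 / 2^13 = 0.0002.

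*Worst rank.* The k non-walkers take the k highest ranks in the direction of worsening. For N = 15 and k = 2 the rank sum for worsening is 14 + 15 = 29. Under the null its mean is 15 × 16 / 4 = 60 and its SD is √(15 × 16 × 31 / 24) = √310 = 17.61. With continuity correction z = (29 − 60 + 0.5) / 17.61 = −1.73, so p ≈ 0.083. The exact distribution also gives 0.083.

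| N | k | p, deleted | p, worst rank (exact) |
|---|---|---|---|
| 15 | 1 | 0.0001 | 0.008 |
| 15 | 2 | 0.0002 | 0.083 |
| 15 | 3 | 0.0005 | 0.33 |
| 30 | 3 | <0.0001 | 0.002 |
| 30 | 5 | <0.0001 | 0.058 |

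At N = 15, two patients are enough to move the result across 0.05. At N = 30 it takes five.

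**Check 2: the other patients are unchanged on average.** Assumptions, none from the protocol: baseline speed mean 1.0 (SD 0.25), change SD 0.12, and non-walkers drawn at random from the same baseline distribution. There were 4,000 simulated trials per setting. The table gives the share with significant worsening.

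| N | k | Deleted | Scored as speed 0 |
|---|---|---|---|
| 15 | 1 | 2% | 4% |
| 15 | 2 | 2% | 9% |
| 15 | 3 | 2% | 15% |
| 30 | 1 | 3% | 5% |
| 30 | 2 | 2% | 7% |
| 30 | 3 | 3% | 11% |

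The mean change shows the omission more directly. With k = 3 of 15 the mean speed change is 0 after deletion and 3/15 × (−1.0) = −0.20, or −20%, when inability is scored.

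**Check 3: no true change, and the k patients who slowed most are deleted.** This is also a stress case, with 20,000 simulated trials. The nominal chance of a false finding of faster walking is 0.025. For k = 1, 2 and 3 it becomes 0.076, 0.153 and 0.245 at N = 15, and 0.055, 0.101 and 0.167 at N = 30.

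**The case against.** The strongest reply is that the protocol excludes nobody. A reader might infer that non-walkers are removed from the test by rule. The documents do not say so: exclusion follows only from silence, and the intention-to-treat sentence points towards inclusion. That is correct, and it limits how the point may be put. It does not close the gap, because that sentence covers drop-outs only, names no method, and gives no value to a patient who attends but cannot walk. The open time point would allow an earlier time to be used, but that time would not record the loss.

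A reader might also infer that loss of walking cannot appear anywhere in the trial, or that the overall efficacy claim is biased. The documents do not support this. HHD at Week 24 covers hip, knee and ankle muscles and codes inability. R-ODS scores walking and stair items down to impossible, and SF-36 asks about walking one block; both are repeated monthly. The secondary end-point counts progression that requires reversion to IVIG, PLEX, other medication or hospitalization. The timed walk is neither the primary efficacy endpoint nor a listed primary or secondary end-point.

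The size can also be challenged, with reason. No rate of lost walking is given. At one or two non-walkers the signed-rank test seldom detects worsening under either rule, and checks 1 and 3 are stress cases.

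Finally, scoring speed as 0 does not guarantee a large negative rank. The change then equals minus the baseline speed. A patient who starts at 0.1 scores −0.1, and with a change SD of 0.12 about 40% of ordinary changes are larger in size (0.1 / 0.12 = 0.83 SD). Since walking impairment is a qualifying feature, slow baseline walkers are likely. This stands, and it favours a worst-rank rule.

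**Conclusion.** The concern holds for the walking result alone. As written, a patient who loses the ability to walk 20 ft either forms no pair or contributes a time from before the loss, and both routes leave the loss uncounted. The direction favours SCIG.

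The size depends on how many patients lose walking, which the documents do not say. With one or two of 15, the chance of detecting worsening is about 2% under deletion and 4% to 9% with speed 0; with three of 15 it is 15%. The scoring rule can decide the conclusion in an extreme but possible case: 2 non-walkers of 15 with all others faster gives p = 0.0002 or 0.083. The effect is smaller at N = 30 than at the 15 patients implied by the recruitment plan, and those two figures should be reconciled.

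This should be corrected, but it does not undermine the primary efficacy comparison.

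**What to change.** Add to Sample size and statistical analysis, before any walk data are examined:

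- The walk at Week 24 is compared with baseline.
- A patient able to walk 20 ft at baseline but unable at Week 24 for neurological reasons stays in the signed-rank test with the worst rank. Walking speed with inability scored 0 is an acceptable alternative, provided the plan notes that it gives smaller ranks to slow baseline walkers.
- The reason is recorded whenever the walk is not done. The walk form is not in the supplied text, so first check whether it already has such a field.
- The number unable to walk is reported at baseline and at Week 24. Patients unable at both times have no change and add nothing to the signed-rank test, so the count is the only place they appear.
- A sensitivity analysis without the worst-rank patients shows how far the result depends on the rule.

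The cost is one analysis sentence, one reason code and a short table, with no new visits and the same test. The walking result may look slightly less favourable.

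### Week 24 strength is compared without regard to rescue, and the secondary endpoint can miss a relapse treated with an IVIG boost and continued SCIG

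*Combined protocol and SAP*

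**What the plan says.** All of the following stands in the combined protocol and SAP, under Approach.

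- **Primary efficacy endpoint (Specific Aim #4).** "For the primary efficacy endpoint, HHD muscle strength measured at Week 24 will be compared to HHD muscle strength measured at baseline (pretreatment"). The same paragraph adds, more generally, "Data from pretreatment and SCIG treatment phase will be compared", without naming a visit, a score or a relapse summary. The statistical section specifies a Wilcoxon paired test at 0.05.
- **Relapse (Rescue protocol).** "Relapse is defined as a 20% decrease in force (as detected on HHD) in more than 50% of the muscles tested", relative to baseline.
- **What follows a relapse.** "In case of relapse, we will quantify the serum Ig levels, give IVIG 1 g/kg boost followed by SCIG at 2 g/kg per month". For a patient already at that dose: "If the subject is already on 2 g/kg per month of SCIG, we will switch the patients back to IV administration", and/or other treatment is started.
- **Other routes back to IVIG (Rescue protocol).** At any point, if "The subject requests the switch due to treatment failure, adverse events or patient preference", or if the investigators judge it best for the patient.
- **Secondary End-Point.** There is one: "Progression of symptoms requiring reversion to IVIG, initiation of PLEX or other medications, or hospitalization".
- **Drop-outs (Potential Pitfalls and Alternative Strategies).** Their data are analysed by intention to treat. Rescue is not mentioned.

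The named Primary End-Points under Specific Aim #2 are withdrawals for side effects and for laboratory abnormalities. Neither records a relapse.

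**The concern.** Aim 4 asks whether SCIG controls the symptoms of CIDP, in an open-label pilot without a control arm. Loss of control during SCIG is the most direct evidence against that claim, and the plan may fail to show it in two places.

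First, the Week 24 comparison sets no condition on what happened before Week 24. If rescue works, a patient who lost strength on SCIG and regained it after a boost and a raised dose, or after a switch, contributes a value near baseline. That value then supports SCIG.

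Second, the secondary endpoint should catch such a patient, but its list of events omits both the dynamometry-defined relapse and the boost. Whether the same fall in strength is an event then depends on the SCIG dose at the time and on how the reader takes two phrases in the endpoint. Two analysts could report different numbers of failures from the same data.

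**Working it through.** The documents give no relapse rate, standard deviation, power calculation or rule for combining muscles, so there is no stated figure to reproduce. The check is a reading of the text, followed by illustrations under stated assumptions.

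**1. Which relapses does the secondary endpoint catch?**

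| Course after a dynamometry-defined relapse | What the Rescue protocol leads to | Named in the secondary endpoint? |
|---|---|---|
| Already at 2 g/kg per month of SCIG | Return to IV and/or other treatment | Yes |
| Below that dose; switched directly for treatment failure | Return to IVIG | Yes |
| Below that dose; boosted, then a second relapse | Now at 2 g/kg per month, so return to IV and/or other treatment | Yes, at the second relapse |
| Below that dose; boosted, continues SCIG, nothing further | IVIG boost, then SCIG at 2 g/kg per month | Only if one boost is read as a reversion to IVIG or as another medication |

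The gap is the last row. The dosing paragraph gives 1 to 2 g/kg per month as the usual maintenance range, and doses above 2 are excluded. Many relapsers may therefore be below 2 when they relapse, but the documents do not give the share.

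**2. Effect on the event count**

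Exact (Clopper-Pearson) 95% limits for x events in n patients: lower = Beta quantile(0.025; x, n − x + 1), upper = Beta quantile(0.975; x + 1, n − x). For x = 0 the lower limit is 0 and the upper is 1 − 0.025^(1/n).

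Assume 6 relapses in 30 and no other named event:

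- boosted relapses counted: 6/30 = 20% (7.7 to 38.6%);
- not counted, half take the boost route: 3/30 = 10% (2.1 to 26.5%);
- not counted, all take it: 0/30, upper limit 1 − 0.025^(1/30) = 11.6%.

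The recruitment plan ("Planned recruitment is an average of 1 patient every 1.5 months, for a total of 22.5 months") gives 22.5 / 1.5 = 15 patients. With 3 relapses the contrast is 3/15 = 20% (4.3 to 48.1%) against 0/15 (0 to 21.8%).

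**3. Effect on the Week 24 test**

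Nine muscle groups tested on both sides make 18 muscles, so more than half means at least 10. If all muscles count equally and the other 8 are unchanged, the mildest qualifying relapse is a mean loss of 10/18 × 20% = 11.1%.

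Assumptions: n = 30, exactly 6 relapsers (SD 5 percentage points), no true change in the other 24 (SD 5, 10 or 15), and a two-sided signed-rank test at 0.05 (the documents do not state sidedness). The lower critical value is W+ ≤ 137, with tail probability 0.0249.

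- Rescue restores baseline: mean change 0; chance of significant worsening about 2.5%.
- No recovery, 11.1% loss: mean change 6/30 × (−11.1%) = −2.2%; chance about 30%, 20% and 14% at SD 5, 10 and 15.
- No recovery, larger losses (relapsers averaging 25 to 37%): about 26 to 37% with exactly 6 relapsers, and 30 to 40% in separate simulations at a 20% relapse rate.

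The no-recovery range at about 6 relapsers is therefore 14 to 40%. The 2.5% is no more than the assumption of full recovery carried through the test.

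**The case against.** The strongest reply is that using the observed Week 24 value is a legitimate treatment-policy comparison. The boost is one dose followed by SCIG, and the dosing paragraph says dosing is individualized by response. After a boost at Week 8, the Week 24 value follows about 16 weeks of SCIG. This stands. The observed comparison should be kept; what is missing is the information needed to interpret it.

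A reader might infer that every relapser below 2 g/kg per month takes the uncounted route. The documents do not support that, because the Rescue protocol also allows a direct return to IVIG at any point. Nor do they support the inference that repeated failure disappears, since a second relapse after the boost leads to a named event. The 0/30 case thus needs all six to be boosted and none to switch, relapse again or start another treatment before Week 24.

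A reader might also infer that early leavers are lost from the comparison. Table 2 makes the last visit a combined Week 24 and early-termination visit with dynamometry, and drop-outs' data are to be used. Together these imply that the early value is analysed. One explicit sentence would settle it, so this is a minor clarification.

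Finally, the test is weak whatever is done. With 6 relapsers in 30 it misses the decline in most trials even without recovery. This is a reason to put the weight on the relapse count rather than on a different Week 24 value.

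The rescue algorithm in Appendix 2 is not readable in the text available here. It is described as a treatment algorithm, so it may not define endpoint events, but this could not be checked.

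**Conclusion.** The point holds, centred on the relapse count. As written, Week 24 strength after rescue or a switch counts toward efficacy. On a literal reading, a single boosted relapse with no later named event appears in neither efficacy endpoint, although the scheduled dynamometry records it.

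The direction needs no assumption: if rescue works, the plan can make SCIG look better than it was. The size does depend on assumptions. The event rate can be understated by the whole proportion of patients with such a relapse, for example 0% instead of 20% with 6 of 30. The effect on the Week 24 test (about 2.5% against 14 to 40%) varies with the relapse rate, loss and SD assumed, and is small if only 10% relapse.

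The documents do not support the stronger conclusion that the Week 24 comparison is invalid. This should be fixed because the repair is cheap and the failure count is central to Aim 4 in an uncontrolled study.

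**What to change.** Change analysis text only; patient care stays as it is.

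1. **Secondary endpoint.** Add every relapse that meets the protocol's dynamometry rule, including one treated with a boost and continued SCIG, and label it protocol-defined relapse.
2. **Proportion.** Report the proportion of all treated patients who are on SCIG at Week 24 without relapse, rescue or switch, with an exact 95% CI. List the reasons separately, so that a switch for preference or adverse events is not read as loss of efficacy.
3. **Week 24 comparison.** Keep it with all observed values. Report how many follow rescue or a switch, state that the early-termination measurement is used for early leavers, and interpret the result together with items 1 and 2.

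Analyses using the last value before rescue, or worst ranks, are optional. Both act on patients selected for a low value and can overstate decline. With no true change, SD 10, independent visits and n = 30, they show false worsening in about 19 to 20% of trials against a nominal 2.5%, falling to about 3% at a between-visit correlation of 0.8.

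**Cost.** A few sentences and slightly more analysis. Dynamometry is already scheduled monthly (Table 2), and concomitant medications are reviewed at all visits (Safety Monitoring and Adverse Events Reporting). The date of first rescue or switch must be kept in the dataset.

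**Downside.** The efficacy result may look less favourable, and the count may include relapses triggered by measurement noise. With no true change and SD 10, the chance of a 20% mean fall at one visit is 2.28%. Over six independent visits that is 1 − (1 − 0.0228)^6 = 13% of patients, or about 6% when visits are strongly correlated. Hence the label in item 1.

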Patients will undergo baseline laboratory studies (CBC, CMP, TSH, quantitative IgG, PT/INR/PTT, pregnancy test for women of productive age), EKG, QOL questionnaires, treatment satisfaction and SE questionnaires, neurological and physical examination, and HHD measurements.

The study will provide all study medications, pumps, and supplies.

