1. CBC with differential count and platelet count will be done prior to treatment and once per month during treatment.
2. Symptom monitoring will be done via phone and at scheduled visits at regular intervals. Study visits will have a window of +/- 7 days. Patients will have 24/7 access to investigators to report any symptoms that develop.
3. Subjects will be provided with emergency contact number for questions relating to any symptoms during the study.
4. In the event that the subject experiences a reaction at home, they will call us. They will also be trained to call 911 in an emergency situation.

Primary End-Points.

1. Significant side-effects requiring withdrawal from study.
2. Laboratory abnormalities requiring discontinuation of study.

**Table 2.** Schedule of Study Events and Visits.

	Screening	Day 1	Week 1	Week 2*	Week 3*	Week 4 (Month 1)	Week 8 (Month 2)	Week 12 (Month 3)	Week 16 (Month 4)	Week 20 (Month 5)	Week 24 EOS/ET (Month 6)	Follow-Up
	V1	V2	V3	V4	V5	V6	V7	V8	V9	V10	V11	V12
Informed Consent	x											
Inclusion/Exclusion Review	x	x										
Medical History	x	x	x									
Vital Signs Monitoring	x	x	x	x	x	x	x	x	x	x	x	
Physical/Neuro Exam	x	x	x			x	x	x	x	x	x	x
TSQM	x	x	x			x	x	x	x	x	x	
CIP-PRO20	x	x	x			x	x	x	x	x	x	
R-ODS	x	x	x			x	x	x	x	x	x	
SF-36	x	x	x			x	x	x	x	x	x	
Hand-held Dynamometry	x	x	x			x	x	x	x	x	x	
20-ft Timed Walk	x	x	x			x	x	x	x	x	x	
Electrocardiogram (ECG)	x											
PT/INR, PTT	x											
TSH	x											
Quantitative IgA, IgG, IgM	x	x				x	x	x	x	x	x	
Hematology, blood chemistry	x		x			x	x	x	x	x	x	x
Urine Pregnancy Test	x	x	x			x	x	x	x	x	x	
Subcutaneous Drug Administration Training	x	x	x	x								
Subcutaneous Drug Administration	x	x	x	x								
Drug Diary Training	x	x										
Drug Diary Review				x	x	x	x	x	x	x	x	
Drug Dispensation	x	x	x	x	x	x	x	x	x	x	x	
Drug Accountability							x	x	x	x	x	

\* optional for additional administration training (can be completed at home)

Specific Aim #3. To test the hypothesis SCIG is associated with better QOL.

At baseline (pretreatment of SCIG, while subjects are being treated with IVIG), QOL and treatment satisfaction questionnaires (SF-36, CIP-PRO20, R-ODS, and TSQM) will be done. These measures will be repeated monthly during the course of the study. Data from pretreatment and treatment with SCIG phase will be compared using appropriate statistical methods with correction for multiple comparisons.

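### Does the Week 24 strength comparison need a named baseline visit, given that dynamometry is scheduled at both Screening and Day 1?

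*Combined protocol and SAP*

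**What the plan says.** Specific Aim #4 defines the primary efficacy comparison: "HHD muscle strength measured at Week 24 will be compared to HHD muscle strength measured at baseline (pretreatment" (the bracket closes there). Just before this it says of HHD and the timed walk together: "Data from pretreatment and SCIG treatment phase will be compared". On technique it adds: "Measurement will be done bilaterally in duplicates".

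The paragraph on sample size and statistical analysis gives the test: "Wilcoxon paired ranked test will be used to compare the change of before and after from each patient". It sets the level at 0.05 and contains no baseline rule.

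Specific Aim #3 comes nearest to a definition: "At baseline (pretreatment of SCIG, while subjects are being treated with IVIG), QOL and treatment satisfaction questionnaires" are to be completed. That describes a period (before SCIG, still on IVIG), not a visit. The work-up under Specific Aim #2 begins "Patients will undergo baseline laboratory studies (CBC, CMP, TSH, quantitative IgG, PT/INR/PTT, pregnancy test for women of productive age), EKG, QOL questionnaires" and ends with HHD, again without naming a visit.

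Table 2 marks HHD, the 20-ft walk, SF-36, R-ODS, CIP-PRO20 and TSQM at Screening, at Day 1 and at seven later visits (Weeks 1, 4, 8, 12, 16, 20 and 24). The Data Management section treats collection as two time points, one before SCIG and one during it. It also says: "There will be an interim analysis done after 8 patients have completed the study".

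**The concern.** The study is single-arm and open label, so any error or shift in the baseline passes straight into each patient's change score; no control group cancels it. Two visits could serve as baseline, and the text does not choose between them. An analyst could compute the Week 24 change from Screening, from Day 1 or from their mean, look at all three and report the most agreeable one. The interim look after 8 completers seems to offer an early chance to do so.

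The choice could cut either way. Patients move from an effective treatment at a 1:1 dose, so a convenient baseline might produce an apparent gain or hide a real decline. The apparent remedy is to fix the rule now, and perhaps to average the two visits for precision.

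**Working it through.** **Inputs.** Sample size: up to 30 (Participants paragraph). The recruitment plan implies 22.5 / 1.5 = 15, so n = 15 is a second case. Test: paired signed-rank at 0.05, taken as two-sided. The documents give no SD, retest reliability or between-visit correlation for HHD and no power calculation, so there is no planned figure to reproduce and everything below is assumption.

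**Model.** Each visit has error variance 1. Let r be the correlation of the Screening and Day 1 errors, and s the SD of true change between patients in visit-error SDs. Three cases are used: (r, s) = (0, 0), (0.5, 1) and (0.8, 2).

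**Step 1: what happens if the visit is chosen after the data are seen?** With no true mean change, the two single-visit change scores correlate at (1 + r + s²)/(2 + s²):
- (0, 0): 1/2 = 0.50
- (0.5, 1): 2.5/3 = 0.83
- (0.8, 2): 5.8/6 = 0.97

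Simulating the exact two-sided signed-rank test gives:

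| Practice | n | (0, 0) | (0.5, 1) | (0.8, 2) |
|---|---|---|---|---|
| Report whichever visit is significant, either direction | 30 | 9.2% | 7.7% | 6.3% |
| Same | 15 | 8.7% | 7.5% | 6.2% |
| Report the visit showing more improvement: false benefit | 30 | 4.6% | 3.9% | 3.1% |
| Same practice: false worsening | 30 | 0.4% | 1.1% | 1.8% |

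The two practices differ. Under the second, total rejections stay near 5% (0.4 + 4.6 = 5.0%, for example). What changes is the split between directions: false benefit rises above its nominal 2.5% and false worsening falls below it.

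**Step 2: what happens if one rule is simply used?** When both visits reflect the same true state, Screening alone, Day 1 alone and the mean each give about 4.7% at n = 15 and 5.0% at n = 30. The plan carried out with any one of them is valid.

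**Step 3: is the mean clearly better?** The variance of change is 2 + s² with one baseline visit and 1 + (1 + r)/2 + s² with the mean. The proportional reduction is R = [(1 − r)/2]/(2 + s²):
- (0, 0): 0.5/2 = 25%
- (0.5, 1): 0.25/3 = 8.3%
- (0.8, 2): 0.1/6 = 1.7%

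The 25% case requires every patient to have the same true change. In the central case, power for an illustrative change of 0.5 SD rises from 73.5% to about 77% at n = 30, and from 41.8% to about 45% at n = 15.

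Now let the nearer visit track Week 24 better. Take unit variances, a Screening–Day 1 correlation of 0.90, a Day 1–Week 24 correlation rD, and a Screening–Week 24 correlation of 0.9 × rD:

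| rD | Day 1: 2(1 − rD) | Screening: 2(1 − 0.9rD) | Mean: 1.95 − 1.9rD | Mean against Day 1 | Mean against Screening |
|---|---|---|---|---|---|
| 0.7 | 0.60 | 0.74 | 0.62 | +3.3% | −16.2% |
| 0.8 | 0.40 | 0.56 | 0.43 | +7.5% | −23.2% |

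**Step 4: what if Screening is systematically shifted?** A first-test learning effect, or a different point in the IVIG cycle, would do this. The mean carries half the shift d. The central-case gain over Day 1 is cancelled in mean squared error when d²/4 = R/n:
- n = 30: d = 2√(0.0833/30) = 0.105, about 0.11 SD of the change
- n = 15: d = 2√(0.0833/15) = 0.149, about 0.15 SD

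In case (0, 0), suppose the state at Week 24 equals that at Day 1 and Screening is shifted by 0.5 to 1 error SD. The mean then rejects in 18 to 56% of trials at n = 30, and Day 1 alone in about 5%. First SCIG is tied to within 2 weeks of the last IVIG course, but the documents give Screening no such interval, so a shift of this kind cannot be excluded.

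**The case for a change.** The best argument for acting is that the cure costs two or three sentences and the endpoint is called the primary efficacy endpoint. It is tested at 0.05 with no control arm. Nor is Day 1 the obvious reading: the baseline work-up groups HHD with TSH, clotting tests and EKG, which Table 2 marks only at Screening. Table 2 reads as aligned on this point, since the blanks in the HHD row fall at the optional Weeks 2 and 3. In the case (0, 0), the two single-visit tests disagree on significance in about 8% of null trials at n = 30. All of that stands as a description of the gap.

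Four things limit it.
- The listed Primary End-Points are safety outcomes, the first being "Significant side-effects requiring withdrawal from study". The study calls itself a pilot.
- The word pretreatment already confines the baseline to values taken before SCIG, so a reading made after the Day 1 infusion does not qualify.
- Nothing says the interim look analyses HHD. If it did, reporting whichever visit is significant at n = 8 gives about 7.3, 6.3 and 5.2% in the three cases, against 3.9% for one fixed visit.
- Naming the visit would close only one route to selection. Nine muscle groups on two sides make 18 sites, tested in duplicate, and the plan does not say how they become one score. That is a separate matter.

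The relapse definition also uses the word baseline; that clinical rule is not judged here.

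**Conclusion.** No change is needed. The baseline visit is unnamed, but the candidates are the same measurement taken before SCIG while the patient is on IVIG, and an analyst would settle on one as a matter of routine. Used consistently, either gives a valid test when the two visits reflect the same state.

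The inflation to about 6 to 9% (either direction), or to about 3 to 4.6% for false benefit against 2.5%, describes selection after the fact. It does not describe the plan as written. These rates rest on assumed error models with no HHD variability data behind them.

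The one concrete alternative, averaging, is a fair trade-off and not a correction. It reduces variance by 1.7 to 25% if both visits track Week 24 equally well, and increases it by 3.3 to 7.5% against Day 1 if they do not. A Screening shift of 0.11 to 0.15 SD cancels its central-case gain. The documents do not show which situation applies, so they give no ground for preferring it.
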